6.10.4.5. Pancreatitis

Summaries of adjudicated and investigator-reported pancreatic events will be provided by each randomized treatment. However, the summary report will only be generated if >3% patients have pancreatic event(s). Determination of investigator-reported events will be through the "Acute pancreatitis" Standardized MedDRA Queries (SMQ) and a "Chronic pancreatitis" Lilly Search Categories (LSC) of the AE database, while adjudication-confirmed pancreatitis will be found from adjudication CRF.

The patients developing pancreatitis will be listed separately for the investigator-reported and the adjudicated events.

Each pancreatic enzyme at Week 26, and the maximum post-dose value will be summarized by each randomized treatment in a shift table using >1x upper limit of normal (ULN), and $\ge 3x$ ULN separately for the mITT population, mITT population with normal baseline, mITT population with baseline value > ULN.

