Study Phase	Screen	Lead - in	Randomize							Treatm	ent Pha	ise					Follow up	Early Term
Visit	1	2	3	4	5	6	7	8	9	10	11	12	13	14	15	16	801	
Week of Treatment	-3	-2	0	1	1	2	2	4	4	8	12	12	16	20	24	26	(30)	
Study day/(Dose number)			0/(1)	7/(2)		14/(3)		28/(5)		56/(9)	84/(13)		112/(17)	140/(21)	168/(25)	182/(27)		
Visit Window (days)		±7				±3		±3		±3	±3		±3	±3	±3	±3	±3	
PK Specific Visit ^a					X		X		X			X						
Study drug and injection supplies, dispense			X	X		X		X		X	X		X	X	X	X		
Health habits (alcohol use yes/no, tobacco use current/past)	X																	
Patient returns unused study drug supplies								X		X	X		X	X	X	X		X
Study drug, assess compliance								X		X	X		X	X	X	X		X
Patient Demographics																		
Age	X																	
Gender	X																	
Race/Ethnicity	X																	
Clinical Variables																		
Physical examination	X															X		X
Symptom-driven physical exam			X					X		X	X		X	X	X	X	X	X
Height	X																	
Weight	X		X	X		X		X		X	X		X	X		X	X	X
Waist circumference	X		X					X		X	X		X	X		X	X	X
Vital signs (BP and PR)	X		X	X		X		X		X	X		X	X		X	X	X
Antidiabetic medication	X	X	X	X		X		X		X	X		X	X	X	X	X	X
Concomitant medication	X	X	X	X		X		X		X	X		X	X	X	X	X	X

Study Phase	Screen	Lead - in	Randomize		Treatment Phase													Early Term
Visit	1	2	3	4	5	6	7	8	9	10	11	12	13	14	15	16	801	
Week of Treatment	-3	-2	0	1	1	2	2	4	4	8	12	12	16	20	24	26	(30)	
Study day/(Dose number)			0/(1)	7/(2)		14/(3)		28/(5)		56/(9)	84/(13)		112/(17)	140/(21)	168/(25)	182/(27)		
Visit Window (days)		±7				±3		±3		±3	±3		±3	±3	±3	±3	±3	
PK Specific Visit ^a					X		X		X			X						
Other																		
ECGs ^b	X		X							X ^c	X ^c	X^{c}				X^{c}	X	X
Evaluation of Injection Site Reactions			X	X		X		X		X	X		X	X	X	X		X
APPADL and IW-SP		X									X					X		Х
questionnaires		Λ									Λ					Λ		Λ
Diagnostics (Safety)																		
Screening Laboratory Tests ^d	X																	
Pregnancy test ^e	X		X															
Estradiol, FSH, LH ^f	X																	
Chemistry panel	X		X					X			X					X	X	X
Lipase and amylase	X		X	X		X		X		X	X		X	X	X	X	X	X
Lipid panel	X		X					X			X					X		X
eGFR	X		X					X			X					X	X	X
Hematology	X							X			X					X	X	X
Urinalysis	X										X					X	X	X
Urine albumin, creatinine, UACR	X										X					X	X	X

Study Phase	Screen	Lead - in	Randomize							Treati	nent Ph	ase					Follow up	Early Term
Visit	1	2	3	4	5	6	7	8	9	10	11	12	13	14	15	16	801	
Week of Treatment	-3	-2	0	1	1	2	2	4	4	8	12	12	16	20	24	26	(30)	

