In addition to the diagnostic assessment in patients who develop symptoms of acute pancreatitis, each patient will have measurements of pancreatic amylase and lipase at screening, baseline, and at each non-PK-specific visit to assess any potential effects of LY3298176 on the exocrine pancreas (refer to Section 2, Schedule of Activities). Further diagnostic assessment per Lilly algorithm for assessment of asymptomatic pancreatic hyperenzymemia will be required whenever lipase and/or pancreatic amylase are ≥3× ULN at any time during the study. If this situation occurs at Visit 801 (Week 30), the patient will be required to undergo this additional workup, and the data will be collected in the clinical trial database.

All suspected cases of acute or chronic pancreatitis, as well as cases of confirmed lipase or pancreatic amylase values ≥3× ULN, will be adjudicated by an independent committee of expert physicians. In addition, AEs of severe or serious abdominal pain of unknown etiology will also be submitted to the adjudication committee to assess for possible pancreatitis or other pancreatic disease. Relevant data from patients with acute or chronic pancreatitis, those with severe or serious abdominal pain, and those that undergo additional assessments due to confirmed hyperenzymemia will be entered into a specifically designed eCRF page by study site or Lilly staff. The adjudication committee representative will enter the results of adjudication in a corresponding eCRF page.

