10.2. Populations for Analyses

For purposes of analysis, the following populations are defined in Table GPGB.5.

Table GPGB.5. Definitions of Populations to Be Analyzed in Study GPGB

Population	Description			
Enrolled	All participants who sign informed consent.			
ITT (intention-to-treat)	All randomized patients.			
mITT (modified ITT)	All randomized patients with at least 1 post-baseline measurement according to the treatment the patients were assigned.			
PP (per protocol)	All randomized patients who were compliant with study drug and completed the protocol.			
Safety	All randomized participants who take at least 1 dose of study treatment. Participants will be included in the treatment group to which they were randomized. In the event of a treatment error, participants will be analyzed according to the treatment they actually received.			

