10.3.4. Safety Analyses

10.3.4.1. Clinical Evaluation of Safety

The safety population will be used for safety analyses. Both the overall and the pairwise comparisons of each LY3298176 dose versus placebo and dulaglutide will be reported for these safety analyses.

Safety measures will include vital signs, body weight, TEAEs (including SAEs and AEs of special interest), laboratory measures (including anti-LY3298176 antibodies), and ECGs. Summary statistics will be presented by treatment for the safety measures.

The summary statistics for continuous variables will be sample size, mean, SD, median, minimum, and maximum.

The summary statistics for categorical variables will be sample size, frequency, and percentage.

Exposure to each therapy during the treatment period of the study will be calculated for each patient and summarized by treatment group.

In addition, the following safety outcomes will be analyzed on the mITT population:

- Change from baseline to 26 weeks in HDL-C, total cholesterol, triglycerides, and LDL-C
- Change from baseline to 12 and 26 weeks in fasting FGF-21, adiponectin, β-hydroxy butyrate, glucagon, and insulin levels
- Percentage of patients requiring rescue therapy

The change from baseline of HDL-C, total cholesterol, triglycerides, LDL-C, fasting FGF-21, adiponectin, β -hydroxy butyrate, glucagon, and insulin levels will be calculated using a similar MMRM-based model to the one used for the primary analysis. The corresponding baseline will be used in the model instead of the baseline HbA1c levels. The MMRM model will also include a term for the HbA1c stratification group.

Additional analysis, such as concentration—safety lab plots, may be performed if warranted upon review of the data.

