4.2. Secondary Objectives

To determine the effect of LY3298176 versus dulaglutide and placebo on:

- mean body weight change from baseline to 12 and 26 weeks
- change from baseline of HbA1c at 12 weeks
- percentage of patients with \geq 5% body weight loss at 26 weeks
- percentage of patients with >10% body weight loss at 26 weeks
- percentage of patients reaching the HbA1c target of \leq 6.5% and of \leq 7.0%
- change from baseline of fasting plasma glucose (FPG) at 12 and 26 weeks
- change from baseline to 26 weeks in high-density lipoprotein cholesterol (HDL-C), total cholesterol, triglycerides, and low-density lipoprotein cholesterol (LDL-C)
- waist circumference
- safety and tolerability, including gastrointestinal (GI) tolerability, incidence and rate of hypoglycemia, hypersensitivity reactions and pancreatic safety.

In addition, it is intended to assess

- the development of treatment-emergent anti-drug antibodies (TE ADA) to LY3298176
- the pharmacokinetics (PK) of LY3298176 and potential patient factors that may influence its PK and pharmacodynamics (PD).
- the relationship between LY3298176 dose and/or exposure and key efficacy, and safety measures, where applicable.

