6.10.4.6. C-cell Hyperplasia and C-cell Neoplasms

Listings of AEs of interest using a LSC will be provided by HLTs thyroid neoplasms, thyroid neoplasms malignant and thyroid disorders. The summary report for these AESIs by each randomized treatment will be reported if there are >3% patients with these AESIs.

Calcitonin data will be summarized using an MMRM model similar to the supportive analyses.

Calcitonin values will be listed for those patients with a post-first dose serum calcitonin increase from baseline $\geq 50\%$ and the absolute value ≥ 20 pg/ml. These patients will be classified by their absolute calcitonin values into the following categories: ≥ 20 and ≤ 25 pg/ml; ≥ 35 and ≤ 50 pg/ml. A shift table using these categories will be generated if the proportion of patients with these changes is $\geq 3\%$.

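### Lipase and amylase are measured at nine on-treatment visits for pancreatic safety, but the SAP names no model-based comparison between arms for them

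*SAP*

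**What the plan says.** SAP Section 4.2 lists among the secondary safety aims "incidence and rate of hypoglycemia, hypersensitivity reactions and pancreatic safety". Protocol Section 9.2.1.2.5 states that "each patient will have measurements of pancreatic amylase and lipase at screening, baseline, and at each non-PK-specific visit", and gives the purpose as "to assess any potential effects of LY3298176 on the exocrine pancreas".

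The analysis is in two places. In SAP Section 6.10.4.5, "the maximum post-dose value will be summarized by each randomized treatment in a shift table using >1x upper limit of normal (ULN", together with a cut at ≥3x ULN and the same summary at Week 26. It is done for the mITT population, for those with normal baseline and for those with baseline above ULN. SAP Section 6.10.5 gives n, mean, SD, median, minimum and maximum of the value and of the change from baseline, by arm and visit, for laboratory measurements in general. It also gives a summary and analysis of treatment-emergent abnormal values. Both enzymes are in the laboratory list (protocol Appendix 2), so these rules cover them. No test, model or interval is named for the enzymes as continuous measures.

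For the next safety topic, SAP Section 6.10.4.6, the text is different: "Calcitonin data will be summarized using an MMRM model similar to the supportive analyses". Protocol Section 10.3.4.1 says of the safety analyses in general: "Both the overall and the pairwise comparisons of each LY3298176 dose versus placebo and dulaglutide will be reported for these safety analyses".

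**The concern.** The enzymes are among the most frequently sampled safety measures in the trial, and they are collected to detect a drug effect on the pancreas. Yet the plan yields no estimate of that effect against placebo or dulaglutide. Pancreatic events are unlikely to fill the gap. SAP Section 6.10.4.5 tabulates them only if more than 3% of patients have one. Read over about 300 randomised patients, 3% is 9, so at least 10 patients are needed, and below that events are only listed. The enzymes may then be the main between-arm evidence on the pancreas in a study meant to support Phase 3 dose selection. Without an estimate and interval, a reader cannot tell a well-excluded rise from one that was poorly measured.

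A smaller matter is the population. The shift table is on mITT by randomised treatment. SAP Table 6.1 presents all safety analyses by actual treatment group, and protocol Table GPGB.5 says: "In the event of a treatment error, participants will be analyzed according to the treatment they actually received".

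**Working it through.** **1. Enzymes beside the other safety measures.** On-treatment visits are counted from the Schedule of Activities. The enzyme visits are 4, 6, 8, 10, 11, 13, 14, 15 and 16.

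| Measure | On-treatment visits | Model named in SAP |
|---|---|---|
| Lipase, amylase | 9 | none (6.10.4.5, 6.10.5) |
| Blood pressure, pulse | 8 | MMRM (6.10.1) |
| ECG HR, PR, QTcF | 4 | MMRM (6.10.6) |
| Lipids | 3 | MMRM (6.10.2) |
| eGFR, creatinine; UACR | 3; 2 | MMRM (6.10.7) |
| Calcitonin | 2 | MMRM (6.10.4.6) |
| ALT, AST, bilirubin | 3 | none (6.10.5) |

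**2. The plan's own figure.** The documents state no power, SD or exceedance rate for the enzymes. The HbA1c figure can be used to check the arm size. With 45 per arm and SD 1.0, SE = √(2/45) = 0.211. For 15 mg against the -0.8% bound with 90% one-sided confidence, power = Φ((1.44 - 0.80)/0.211 - 1.28) = Φ(1.75) = 96.0%. At least one of four doses, simulated 400,000 times with independent arm means, gives 98.3%, against about 98% stated. So 45 per arm is carried forward, with two-sided 5% from SAP Section 6.1.

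**3. One measurement, one dose against placebo, true rise of 0.5 SD (assumed).** Continuous power = Φ(0.5/0.211 - 1.96) = Φ(0.41) = 66%. If a fraction p0 of placebo patients lies above a cut at c (in SD units), the active fraction is p1 = 1 - Φ(c - 0.5). The relative efficiency of the cut is φ(c)²/[p0(1 - p0)].

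| p0 | p1 | Efficiency | Power of counts, if tested |
|---|---|---|---|
| 30% | 49.0% | 0.58 | 45.4% |
| 20% | 36.6% | 0.49 | 41.6% |
| 10% | 21.7% | 0.34 | 32.9% |
| 5% | 12.6% | 0.22 | 24.5% |
| 1% | 3.4% | 0.07 | 11.7% |

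**4. Dose trend over nine visits.** This was simulated 3,000 times per setting for placebo and four doses, 45 each. All enzyme inputs are assumptions:
- log SD 0.4-0.5 and within-patient correlation 0.6;
- 5-20% of untreated values above ULN;
- 0, 10, 60, 85 and 100% of the top-dose rise at 0, 1, 5, 10 and 15 mg.

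Log values were regressed on dose and baseline. Counts were tested with the Cochran-Armitage trend test.

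| Analysis | 15% rise | 25% rise | 40% rise |
|---|---|---|---|
| Log value, mean of nine visits | 85-97% | over 99% | 100% |
| Log value, Week 26 | 51-73% | 88-98% | over 99% |
| Maximum >1x ULN | 28-46% | 60-83% | 93-99% |
| Week 26 >1x ULN | 13-33% | 29-67% | 58-96% |
| Maximum ≥3x ULN | 0-7% | 0-13% | 0-31% |

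With no effect, rejection was 4.2-6.2%, except at 3x ULN (0-1.9%). The simulation applies the full rise from the first visit, although two arms are titrated, so the nine-visit mean is favoured. The Section 6.1.1 MMRM reports each week, so the Week 26 row is the fairer guide to what it would deliver.

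**5. Pairwise check.** A separate simulation compared one dose with placebo for a 25% rise. It assumed a placebo geometric mean of 0.5-0.7x ULN and log SDs of 0.35-0.40 between patients and 0.25-0.35 between visits. Across two runs, power was 65-92% for baseline-adjusted Week 26 log values, 44-65% for maximum >ULN, 26-47% for Week 26 >ULN, and 0-9% for ≥3x ULN.

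**The case against.** The strongest reply is that SAP Section 6.10.5 and protocol Section 10.3.4.4 already show the enzymes as continuous data by arm and visit, and the SAP includes change from baseline. That stands. A reader might infer that the enzymes are compared only as counts, or that a rise within the normal range would be invisible. Neither is so.

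A reader might also infer that the cuts discard most of the power, or that a dose-related rise would more likely be missed than found. The documents do not support either as a general statement. No test is named for the shift table, so it has no planned power to lose. Every enzyme input above is assumed. At 1x ULN the loss runs from more than half (15% rise, maximum against nine-visit mean) to almost nothing (40% rise). For a 25% rise, the maximum >ULN trend test succeeds in 60-83% of simulated trials. Nor does the entry exclusion above 2x ULN show that most patients start below 1x ULN. SAP Section 6.10.4.5 itself plans a table for baseline above ULN.

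The 3x cut is not arbitrary: protocol Section 9.2.1.2.5 uses it for diagnosis, further work-up and adjudication. ALT, AST and bilirubin also have no model, so the enzymes are not unique. These points justify keeping the tables. They do not supply the missing between-arm estimate.

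On the population, SAP Section 6.10 uses actual treatment unless specified, and Section 6.10.4.5 does specify. But SAP Table 6.1 makes no such exception, and the mITT safety outcomes listed in protocol Section 10.3.4.1 do not include the enzymes. In practice, counts should differ only for a patient given the wrong treatment, because the post-dose columns need a post-baseline value anyway. No rate of such errors is given.

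**Conclusion.** The point holds as a gap in the analysis plan with a cheap remedy. It does not show that an enzyme effect would go unseen. For a named safety objective with nine on-treatment measurements, the SAP specifies no baseline-adjusted comparison of each dose with placebo and dulaglutide. It does specify a model for most comparable measures, and the protocol says that pairwise comparisons will be reported.

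The comparison of sections needs no assumptions. The size of the information loss does: it depends on enzyme variability, on the share of patients above ULN and on the true rise, none of which the documents give. Over the ranges tried, the loss is near total at 3x ULN, large at 1x ULN for rises of about 15%, and small for rises of about 40% on the maximum value. The population mismatch is a minor inconsistency to be reconciled.

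**What to change.** In SAP Section 6.10.4.5, add the Section 6.1.1 MMRM on log lipase and log amylase, with the baseline log value as covariate. Back-transform to give, at each visit, the ratio to baseline in each arm and the ratio of each LY3298176 dose to placebo and to dulaglutide, with 95% CIs. Keep the shift tables at both cuts.

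State one population for the section. The safety population by treatment actually received agrees with SAP Table 6.1 and protocol Table GPGB.5. If mITT by randomised treatment is intended, say so as a deliberate exception and give the reason.

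The cost is about two SAP sentences and re-use of an existing program on two analytes already collected. The downside is a few more safety tables with intervals unadjusted for multiplicity, as the SAP already accepts elsewhere.

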6.10.4.6. C-cell Hyperplasia and C-cell Neoplasms

Listings of AEs of interest using a LSC will be provided by HLTs thyroid neoplasms, thyroid neoplasms malignant and thyroid disorders. The summary report for these AESIs by each randomized treatment will be reported if there are >3% patients with these AESIs.

Calcitonin data will be summarized using an MMRM model similar to the supportive analyses.

Calcitonin values will be listed for those patients with a post-first dose serum calcitonin increase from baseline $\geq 50\%$ and the absolute value ≥ 20 pg/ml. These patients will be classified by their absolute calcitonin values into the following categories: ≥ 20 and ≤ 25 pg/ml; ≥ 35 and ≤ 50 pg/ml. A shift table using these categories will be generated if the proportion of patients with these changes is $\geq 3\%$.

6.10.5. Laboratory Measurements

Laboratory measurements by treatment group at each scheduled time of assessment during the treatment and follow-up periods and including any off-treatment safety follow-up visits that occur after discontinuation of study treatment, will be summarized using descriptive statistics. Descriptive statistics for laboratory analyses with continuous results will include sample size, mean, SD, median, minimum, and maximum for both actual values and change from baseline. Laboratory analyses with categorical responses by visit and treatment group will be summarized using sample size, frequency, and percentage.

A listing of laboratory measurements for individual patients by visit will be presented. An additional listing for all laboratory measurements that are outside the normal range will be presented. All laboratory measures that meet the criteria for a listing, including unscheduled and repeat or multiple measurements will be reported.

A summary report and analysis for treatment-emergent abnormal laboratory values (outside the reference ranges as appropriate) for each continuous analyte by treatment will be provided. Shift tables of the change from baseline value to the maximum/minimum postbaseline value to Week 26 for selected analytes using clinically meaningful thresholds will be summarized. A shift table for ALT, AST, total bilirubin, and direct bilirubin will be generated using cutoff \leq 1 ULN, (>1 ULN and <3 ULN), (\geq 3 ULN and <5 ULN), (\geq 5 ULN and <8 ULN), \geq 8 ULN.

A listing of ALT, AST, and total bilirubin values at all visits for all patients who meet any of the following criteria will be presented:

- Alanine aminotransferase (ALT) $\geq 3 \times ULN$
- Aspartate aminotransferase (AST) $\geq 3 \times ULN$

- Total bilirubin $\ge 2 \times ULN$
- ALT or AST $\ge 3 \times ULN$ and total bilirubin $\ge 2 \times ULN$.

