8.1. Discontinuation from Study Treatment

8.1.1. Permanent Discontinuation from Study Treatment

Discontinuation of the investigational product for abnormal liver tests **should be considered** by the investigator when a patient meets one of the following conditions after consultation with the Lilly-designated medical monitor:

- Abnormal liver tests or when a patient meets one of the following conditions:
 - o ALT or aspartate aminotransferase (AST) >8× ULN
 - o ALT or AST >5× ULN for more than 2 weeks
 - ALT or AST >3× ULN and total bilirubin level >2× ULN or prothrombin time >1.5× ULN
 - o ALT or AST >3× ULN with the appearance of fatigue, nausea, vomiting, right upper-quadrant pain or tenderness, fever, rash, and/or eosinophilia (>5%)
 - o Alkaline phosphatase (ALP) >3× ULN
 - \circ ALP >2.5× ULN and total bilirubin >2x ULN
 - o ALP >2.5× ULN with the appearance of fatigue, nausea, vomiting, right quadrant pain or tenderness, fever, rash, and/or eosinophilia (>5%)
- Investigator Decision
 - the investigator decides that the patient should be discontinued from the study medication
- Any medication for weight loss is given for more than 1 week
- Adverse Event
- When any one of the following events occur, Lilly or its designee is to be alerted immediately:
 - o Pancreatitis or pancreatic cancer (refer to Section 9.2.1.2.5 for details)
 - o Estimated glomerular filtration <30 mL/min
 - Any severe injection site reaction or 2 or more moderate injection site reactions occurring a week or more apart
 - o Any significant study drug-related hypersensitivity reaction
 - Any nonfatal major cardiovascular (CV) events (refer to Section 9.2.1.2.6 for details)
 - Any other treatment-emergent adverse event (TEAE), SAE, or clinically significant laboratory value for which the investigator believes that permanent study drug discontinuation is the appropriate measure to be taken.
- If the patient, for any reason (including protocol-mandated institution of rescue therapy; see Section 7.8.1), requires treatment for greater than 1 week with another therapeutic agent that has been demonstrated to be effective for treatment of diabetes. Also, a change in dose of metformin is not allowed (except for incidences of hypoglycemia; see Section 7.1). However, a change to an equivalent dose strength from immediate-release to extended-release (or vice versa) formulation is allowed.

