9.4.4. Safety Monitoring

Lilly will periodically review evolving aggregate safety data within the study by appropriate methods. In addition, the study team will review safety reports in a blinded fashion according to the schedule provided in the Trial-Level Safety Review plan. Lilly will also review SAEs within time frames mandated by company procedures. The Lilly CRP/CRS will, as appropriate, consult with the functionally independent Global Patient Safety therapeutic area physician or clinical scientist.

In addition, specific safety measures are included in the protocol to ensure appropriate monitoring of pancreatic, thyroid, and liver safety. Laboratory findings that trigger pancreatic and thyroid safety monitoring per Lilly standards are provided in Sections 9.2.1.2.5 and 9.2.1.2.7, respectively. Details of liver safety monitoring are provided in Section 8.1.1. If a study patient experiences elevated ALT $\geq 3 \times$ ULN or elevated total bilirubin $\geq 2 \times$ ULN, clinical and laboratory monitoring should be initiated by the investigator. Details for hepatic monitoring depend upon the severity and persistence of observed laboratory test abnormalities. To ensure patient safety and comply with regulatory guidance, the investigator is to consult with the Lilly CRP/CRS regarding collection of specific recommended clinical information and follow-up laboratory tests (see Appendix 4).

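### SAP 6.10.5 grades total bilirubin on aminotransferase cut-points, so the by-arm shift table cannot show how many patients reached the plan's own threshold of 2 × ULN, and the combined ALT/AST and bilirubin criterion has no by-arm count

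*SAP*

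**What the plan says.** SAP 6.10.5 (Laboratory Measurements) plans: "A shift table for ALT, AST, total bilirubin, and direct bilirubin will be generated using cutoff" points that give five categories: ≤1, >1 to <3, ≥3 to <5, ≥5 to <8 and ≥8 × ULN. All four analytes share them.

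The same section plans a by-patient output: "A listing of ALT, AST, and total bilirubin values at all visits for all patients who meet any of the following criteria". There are four criteria: ALT ≥3 × ULN, AST ≥3 × ULN, total bilirubin ≥2 × ULN, and ALT or AST ≥3 × ULN together with total bilirubin ≥2 × ULN.

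In the protocol:

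- Section 9.4.4 says that "specific safety measures are included in the protocol to ensure appropriate monitoring of pancreatic, thyroid, and liver safety". At ALT ≥3 × ULN or total bilirubin ≥2 × ULN, "clinical and laboratory monitoring should be initiated by the investigator".
- Section 8.1.1 lists conditions for considering permanent discontinuation of study drug. One is "ALT or AST >3× ULN and total bilirubin level >2× ULN or prothrombin time >1.5× ULN"; another combines ALP above 2.5 × ULN with total bilirubin above 2 × ULN. For ALT or AST alone the limits are above 8 × ULN, or above 5 × ULN for more than 2 weeks.

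**The concern.** A graded shift table is the by-arm display from which a reader would expect to see whether liver abnormalities differ by dose. It does that when its edges fall where the plan places its clinical limits. For ALT and AST they do. For total bilirubin the plan uses 2 × ULN in three places, and the table has no edge there.

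The combination of raised aminotransferases with raised bilirubin has a related problem. The plan singles it out in Protocol 8.1.1 and in the SAP listing, but specifies no count of it by arm.

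Liver is one of three organ topics for which the protocol claims specific monitoring. What is at stake is whether the report shows, arm by arm, how many patients crossed the plan's own bilirubin limits without the reader counting them from a listing.

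**Working it through.** The plan gives no figure to reproduce here. The check sets the table's edges against the plan's limits.

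**Step 1: edges against limits.** The table's edges are 1, 3, 5 and 8 × ULN. The ALT/AST limits of 3, 5 and 8 (Protocol 8.1.1) are all among them. The bilirubin limit of 2 is not.

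**Step 2: where bilirubin values fall.**

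| Total bilirubin (× ULN) | SAP category | Category with an edge at 2 | Meets listing criterion (≥2) |
|---|---|---|---|
| 1.1 | >1 to <3 | >1 to <2 | no |
| 1.9 | >1 to <3 | >1 to <2 | no |
| 2.0 | >1 to <3 | ≥2 to <3 | yes |
| 2.5 | >1 to <3 | ≥2 to <3 | yes |
| 2.9 | >1 to <3 | ≥2 to <3 | yes |
| 3.0 | ≥3 to <5 | ≥3 to <5 | yes |

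A patient who goes from 1.1 to 2.9 × ULN (a rise of 2.9 − 1.1 = 1.8 × ULN) is shown as no shift. One who goes from 2.9 to 3.0 is shown as a shift. A baseline slightly above 1 × ULN is possible: Exclusion Criterion 15 (Protocol 6.2) limits ALT and excludes known liver disease, but no entry criterion sets a bilirubin limit.

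**Step 3: what the table can say about ≥2 × ULN.** Let n be the number in an arm whose maximum lies in the >1 to <3 cell, and m the number at ≥3 × ULN. The number at ≥2 × ULN lies between m and m + n, and the table cannot narrow it further. With 300 patients in 6 arms, an arm has 300/6 = 50, and each patient is 1/50 = 2 percentage points. Taking m = 0:

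| n (illustrative) | Bounds on the share at ≥2 × ULN |
|---|---|
| 1 | 0% to 2% |
| 2 | 0% to 4% |
| 3 | 0% to 6% |
| 5 | 0% to 10% |

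With an edge at 2 × ULN the number is exact: it is the sum of the categories from 2 upward. The documents give no expected rate of bilirubin elevation, so the values of n are assumptions.

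**Step 4: the combination.** Call the listing criteria A (ALT ≥3), B (AST ≥3), C (total bilirubin ≥2) and D ((A or B) and C). D implies C, so any of A, B, C or D is the same set as any of A, B or C. The fourth criterion adds no patient and produces no separate count. Shift tables for single analytes show each margin but not the joint event. No other output named in SAP 6.10.5 gives a by-arm count of D.

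**Step 5: practice elsewhere in the SAP.** Pancreatic enzymes are tabulated by arm at ≥3 × ULN (6.10.4.5), the level that triggers a work-up in Protocol 9.2.1.2.5. Creatinine has its own edges at 1, 2 and 4 × ULN (6.10.7), and QTcF is summarised at 450, 480 and 500 msec (6.10.6). Putting bilirubin on the ALT and AST edges departs from that practice.

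**The case against.** The strongest reply is that the plan already uses the 2 × ULN threshold where it counts. Every patient at or above it enters the listing, with values at all visits, and that is more than a shift cell shows. In a trial of about 300 patients, counting listed patients is little work. The descriptive statistics also give the maximum by arm at each visit, so an arm whose maxima all lie below 2 × ULN has a count of zero at scheduled visits. Protocol 10.3.4.4 asks only for shifts within and outside reference ranges, so the SAP already goes further than it must. The limits in Protocol 8.1.1 guide patient management and need not become table thresholds. Finally, any cut-point hides changes within a cell: after the split, 1.1 to 1.9 would still be no shift.

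Most of this stands. It rules out a stronger reading that a reader might infer, namely that patients with bilirubin of 2 to <3 × ULN, or with the combination, would be missed. They would not. The bounds in Step 3 describe the shift table alone, not everything the report will contain. The reply does not show that aminotransferase edges suit bilirubin. Once a graded by-arm table is planned, the plan's own threshold is the natural place for an edge.

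A reader might also infer that ALP is left out, because it has its own limits in Protocol 8.1.1 (for example, "Alkaline phosphatase (ALP) >3× ULN") and no place in the liver listing. The documents do not support that. ALP falls under the descriptive statistics, the general listings and "A summary report and analysis for treatment-emergent abnormal laboratory values (outside the reference ranges as appropriate) for each continuous analyte by treatment". The plan for "Shift tables of the change from baseline value to the maximum/minimum postbaseline value to Week 26 for selected analytes using clinically meaningful thresholds" leaves room for more. ALP is also not a monitoring trigger in Protocol 9.4.4.

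**Conclusion.** The point holds as a minor gap in by-arm safety tabulation. The total bilirubin part of the shift table uses edges that do not include the plan's own threshold, so it bounds the by-arm number at ≥2 × ULN without giving it. The combined ALT/AST and bilirubin criterion has no by-arm count.

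The width of the bound equals the number in the pooled cell, at 2 percentage points per patient. This assumes equal arms of 50 and makes no assumption about how common such elevations are. If no patient falls between 1 and 3 × ULN, nothing is lost from the bilirubin table.

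The claim does not extend to patient management, which follows the protocol's triggers, or to the efficacy analyses.

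**What to change.** In SAP 6.10.5:

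1. For total bilirubin, replace the >1 to <3 × ULN category with >1 to <2 and ≥2 to <3 × ULN. This matches Protocol 9.4.4 and the SAP listing. Direct bilirubin can stay as it is, since the protocol sets no limit for it.
2. Report, by arm, the number of patients with ALT or AST ≥3 × ULN and total bilirubin ≥2 × ULN, and state whether the two must occur at the same visit.

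The cost is one extra category and one extra count, with sparse cells likely. No new data are needed: the analytes are in the chemistry panel (Protocol Appendix 2), taken at screening, baseline, Weeks 4, 12 and 26, follow-up and early termination. The count does not cover the prothrombin-time alternative in Protocol 8.1.1. That test is not in the routine panel and appears among the follow-up hepatic tests in Appendix 4.

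An ALP output is optional and not part of this point. If ALP is added as a stand-alone listing trigger, use the protocol's limit of above 3 × ULN. Protocol 8.1.1 applies 2.5 × ULN only in combination with raised bilirubin or with symptoms or eosinophilia.
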